9. Subjects with history of another primary cancer, with the exception of: a) curatively resected non-melanoma skin cancer; b) curatively treated cervical carcinoma in situ; or c) other primary solid tumor with no known active disease present in the opinion of the investigator will not affect patient outcome in the setting of current FLC diagnosis.

TEST PRODUCT(S), DOSE AND MODE OF ADMINISTRATION: ENMD-2076 is provided as hard gelatin capsules containing 50 mg of drug.

Patients will receive a daily oral dose (fasting) of ENMD-2076 of 150, 200 or 250 mg/day based on body surface area.

DURATION OF TREATMENT: Following the Screening and Baseline Period (Day -28 to 1) each treatment cycle will consist of a 4-week Treatment Period (Cycle 1 to Cycle 6+). Patients will be treated until disease progression, unacceptable toxicity or death.

DISCONTINUATION FROM TREATMENT:

The Investigator or the Sponsor may discontinue individual patients from the study at any time. Patients will be encouraged to complete the study; however, they may voluntarily withdraw at any time. The Investigator or designee will document the reason for discontinuation. Patients who went off therapy without evidence of disease progression will have CT scans every two months until disease progression or death.

A patient will be withdrawn from treatment for the following reasons:

- ∞ Significant adverse event
- ∞ Pregnancy
- ∞ Disease progression
- ∞ Consent withdrawn
- ∞ Noncompliance

PRIMARY EFFICACY ENDPOINT:

Overall response rate based on RECIST v 1.1 criteria will be used to evaluate response every two months after first study drug administration. Patients who go off therapy without evidence of disease progression will have CT scans every two months until progression.

SECONDARY EFFICACY ENDPOINTS:

- ∞ Progression-free survival rate at 6 months (PFS6).
- ∞ The median PFS or TTP as based on RECIST 1.1 and measured by time from first study drug administration

until progression or death.

- ∞ The median overall survival as measured by time from first study drug administration to death or study completion.
- ∞ Safety data will be collected from time of informed consent through study completion /withdrawal up to 30 days after the last dose of study medication by each subject.

SAFETY ENDPOINTS:

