6. INVESTIGATIONAL PLAN

6.1 Overall Study Design and Plan – Description

This is a Phase 2 multi-center, open label study in 29 FLC patients. Patients will receive a daily oral dose (fasting) of ENMD-2076 as a single treatment agent. The starting dose will be based on body surface area. If adverse events, two dose reductions at the discretion of the investigator will be allowed for each patient. If adverse events resolve, the dose can be increased in 50 mg increments as tolerated. Dosing interruptions/delays will be allowed at the discretion of the investigator for recovery from adverse events or inter-current illness, particularly if the patient is benefiting from ENMD-2076 treatment. After a treatment interruption for adverse events, treatment can be resumed at a lower dose and increased in 50 mg increments as tolerated. Patients may be treated until disease progression or unacceptable toxicity.

Once a potential patient has been identified and signed the informed consent form, the screening and baseline visit procedures will be completed. Following the baseline visits, patients meeting all study entry criteria will start Cycle 1 and get their first dose of ENMD-2076. Each cycle of treatment consists of a 4-week treatment period. Patients who complete the initial cycle of therapy (4 weeks of treatment) without evidence of significant toxicity or clinical evidence of progressive disease may receive additional 4-week cycles of treatment.

Patients who discontinue therapy for any reason other than progression will continue to receive imaging until progression or death. All recruited subjects will be followed for safety and overall survival.

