6.3.3 Removal of Subjects from Therapy or Assessment

The Investigator or the Sponsor may discontinue individual patients from the study at any time. Patients will be encouraged to complete the study; however, they may voluntarily withdraw at any time. The Investigator or designee will document the reason for discontinuation. Patients who went off therapy without evidence of disease progression will have CT scans every two months until disease progression or death.

A patient will be withdrawn from treatment for the following reasons:

∞ Significant adverse event:

If a patient suffers an AE that, in the judgment of the Investigator, the Sponsor, or the Medical Monitor, presents an unacceptable consequence or risk to the patient, whether or not the AE is considered related to study medication, the patient will be withdrawn from treatment.

∞ Pregnancy

If a female patient becomes pregnant at any time during the study, she will be discontinued from further participation and treatment. See [Section 8.3.7](#) for further information on recording and follow-up of pregnancies.

∞ Disease progression:

Progression by RECIST v. 1.1 criteria, unless in the judgement of the investigator the patient has derived benefit from the treatment.

∞ Consent withdrawn:

The patient chooses to terminate participation in the study.

∞ Noncompliance

Failure to receive or refusal of study medication.

Failure to comply with protocol requirements. The patient has a serious deviation from the protocol that would compromise the integrity of the study data. All occurrences of noncompliance must be documented on the appropriate CRF pages.

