Second Occurrence	
∞ Hold dose until toxicity resolves to \leq Grade 1 or baseline (maximum 14 days).∞ If the patient is benefiting from treatment but toxicity does not resolve to \leq Grade 1 or baseline within 14 days of discontinuation of study drug, then study drug treatment may be delayed for an additional week. If toxicity persists despite additional week off drug, then study drug will be discontinued permanently.∞ If the toxicity resolves to \leq Grade 1 or baseline within 14-21 days then restart dosing at a dose level -2 (150mg/day)
Third Occurrence	
∞ Discontinue study medication.∞ If patient is benefiting from therapy, discuss with PI.

Each cycle of treatment consists of a 4-week treatment period. Patients who complete the initial cycle of therapy (4 weeks of treatment) without evidence of significant toxicity or clinical evidence of progressive disease may receive additional 4-week cycles of treatment.

If any individual patient develops $\geq 2+$ proteinuria on qualitative assessment of protein on urinalysis, then a spot urine protein:creatinine ratio will be obtained, and a 24-hour urine collection will be obtained for quantification. If the spot protein:creatinine ratio remains equal to or below 1, then patients may continue to receive study drug until the 24-hour urine collection is complete (no longer than one week is allowed). If 24-hour urine shows greater than 3.5 g protein/24 hours then study drug will be held until the a repeat study shows a 24-hour urine below 3.5g.

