9. STUDY PROCEDURES AND FLOW CHART

A brief description of the chronological flow of the study is provided in the following sections.

A detailed time and event schedule is provided in [Table 4](#). Time 0 is defined as the precise time of the first ENMD-2076 administration on Day 1. All other time points in this study are relative to these definitions.

Screening Period (Day -28 to Day 1):

Prior to the initiation of any protocol-specific screening assessments not generally performed as part of routine patient care; the patient must be given a complete explanation of the purpose and evaluations of the study. Subsequently, the patient must sign and receive a copy of an Informed Consent Form that was approved by the IRB. Once informed consent has been obtained, the eligibility of the patient will be determined, and Screening Period assessments will be performed.

Treatment Period (before dosing on Day 1 up to Day 28):

On Day 1 before the initiation of the treatment, patients will be evaluated and baseline values for the specific assessments will be obtained. Thereafter during the initial Treatment Period, patients will visit the clinic for evaluation of tolerability, safety, and efficacy. Evaluation visits will be scheduled as described in [Table 4](#).

Table 4 Schedule of Assessments

Measurement/Treatment	Screening	Baseline	Follow-up after study drug administration ^a					Subject Discontinuation ¹
	Days -28 to 1	Day 1 (prior to dose)	Cycle 1			Cycle 2	Cycle 3 +	
			Day 1	Day 8	Day 15	Day 1 (day 29)	Day 1 (of Cycle 3+)	
Inclusion/Exclusion	X	X						
Informed Consent and HIPAA Authorization	X							
Medical/Cancer History	X							
Echocardiogram or MUGA	X					X ^j	X ^j	X ^j
Physical Examination ^c	X	X ^b				X	X ⁱ	X
Vital Signs (HR, temp, RR, BP)	X	X ^b		X	X	X	X ⁱ	X
12-lead ECG	X	X ^b	X ^m			X ^m	X ^{m,n}	X
ECOG Performance Status	X	X ^b				X	X	X
RECIST Assessment	X						X ^k	X
Histological ^q or cytological evidence for diagnosis	X							
Archived specimens for biomarker analyses and genomic testing ^r	X							
Tumor Biopsy ^s for subsequent biomarker analyses	X						X	X
Retained Plasma Sample with biopsy ^t	X						X	X
Hematology ^c	X	X ^b		X	X	X	X	X
Clinical Chemistry ^c	X	X ^b		X	X	X	X	X
Coagulation Tests ^c	X	X ^b					X ^j	
TSH level	X	X ^b				X		
Urinalysis ^{c,d}	X	X ^b				X		X
Pregnancy Test ^e	X	X ^b				X		
Dispense ENMD-2076			X			X	X ⁱ	
Tumor Marker AFP ^f		X				X	X ^k	X
Ammonia		X				X	X ^k	X

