CT ^g (or MRI) of chest, abdomen, pelvis	X						X ^g	X
AE Monitoring		X	X	X	X	X	X ⁱ	X
Concomitant Medications	X	X	X	X	X	X	X ⁱ	X
Follow-up Phone calls								X ^p
Retained Plasma Sample Pharmacokinetics ^o			X	X	X	X	X	

AE = adverse event; BP = blood pressure; DCE-MRI = dynamic contrast enhanced magnetic resonance imaging; HIPAA = Health Insurance Portability and Accountability Act; HR = heart rate; RR = respiratory rate; TSH = thyroid stimulating hormone.

- a. Each visit following Day 1 must be completed with ± 3 days of the indicated visit day and each monthly visit must be completed within ± 7 days of the indicated visit day.
- b. Repeated only if more than 72 hours since screening assessments.
- c. Specific tests are listed in the protocol.
- d. If a patient develops 2^+ proteinuria, then a 24-hour urine collection is required for quantification and a repeat urinalysis should occur every week until resolution.
- e. Women of childbearing potential only.
- f. Tumor markers need to be assessed within 3 days of Cycle 1 Day 1, on Cycle 2, Cycle 3, Cycle 5, etc, and at the end of treatment, but optional on even cycles after Cycle 2.
- g. Baseline scans must be done within 28 days prior to entering study and performed two months after Cycle 1 Day 1 and every two months after (\pm 7 days window). CT Scan can be either liver tri-phasic or liver 4-phase but should be consistent throughout the study.
- h. AEs and concomitant medications are monitored continually while on study. (Patients are instructed to call with AE symptoms between scheduled visits).
- i. Completed on Day 1 at each new cycle.
- j. Completed if clinically indicated and by discretion by the Investigator.
- k. Completed at Cycle 2 and every 2 cycles after baseline (ie. Day 1 of Cycle 3, Cycle 5, etc).
- l. These procedures should be done if a patient reaches disease progression (which may occur at a scheduled visit) or if a patient withdraws for other reasons. For subjects that withdraw for other reasons a CT scan is required every two months until disease progression or death.
- m. Electrocardiogram should be performed on Day 1 of each Cycle pre-dose and 4-6 hours post dose.
- n. For Cycle 4 and beyond, Electrocardiogram may be omitted if all previous ECGs have been clinically insignificant by investigator discretion.

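### After Day 29, Table 4 schedules no urinalysis until discontinuation, so the Section 7.4 proteinuria hold has no scheduled trigger for late-onset proteinuria

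*Combined protocol and SAP*

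**What the plan says.** **Schedule.** The Urinalysis row of Table 4 (Section 9) is marked at Screening, at Baseline (repeated only if more than 72 hours have passed since screening), at Cycle 2 Day 1 (Day 29) and at Subject Discontinuation. The Cycle 1 Day 1, Day 8 and Day 15 cells and the Cycle 3+ cell are empty. Footnote d covers a patient who has already developed 2+ proteinuria: "then a 24-hour urine collection is required for quantification and a repeat urinalysis should occur every week until resolution". Footnote l places the discontinuation assessments at progression or withdrawal: "These procedures should be done if a patient reaches disease progression".

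**Dosing rule.** Section 7.4 applies to any patient who reaches 2+ or more "proteinuria on qualitative assessment of protein on urinalysis, then a spot urine protein:creatinine ratio will be obtained", along with a 24-hour collection. It continues: "If 24-hour urine shows greater than 3.5 g protein/24 hours then study drug will be held", and dosing waits for a repeat below that level. The rule carries no time limit.

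**Duration.** The Synopsis describes 4-week cycles running to Cycle 6 and beyond. Section 6.1 says: "Patients may be treated until disease progression or unacceptable toxicity". Section 6.3.3 lists progression as a reason to stop drug, with an exception: "Progression by RECIST v. 1.1 criteria, unless in the judgement of the investigator the patient has derived benefit from the treatment".

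**The concern.** The plan treats urine protein as a dosing matter. Exclusion criterion 8 screens for it and Section 7.4 sets a numeric threshold for holding drug. Yet the only routine urinalysis between the first dose and the discontinuation column falls on Day 29, and the Section 7.4 rule starts from a urinalysis result.

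A site following the plan exactly could therefore keep dosing a patient with silent proteinuria that began after Day 29, and not reach the hold rule until the patient progresses or withdraws. At that visit a hold matters only for patients kept on drug after progression under Section 6.3.3.

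There is a smaller reporting consequence. Section 10.5.2 summarises laboratory results by time point and as shifts from baseline. For urine protein, that summary would have one scheduled on-treatment time point before discontinuation.

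**Working it through.** **1. Is the Cycle 3+ cell really blank?** The Urinalysis row has eight cells under eight column headings, so the entries have not shifted sideways. Of the rows in Table 4, 16 are marked at Cycle 2. Thirteen of these also carry a mark in their own Cycle 3+ cell: echocardiogram/MUGA, physical examination, vital signs, ECG, ECOG status, hematology, chemistry, dispensing, AFP, ammonia, AE monitoring, concomitant medications and the PK sample. Three do not: TSH, urinalysis and pregnancy test. A true blank is the plainer reading.

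**2. Does any other text supply a routine test?**

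- Section 8.3.1 refers to Table 2, which lists analytes and gives no visit times.
- Section 9.1.2 sends timing back to Table 4.
- Section 9.1.3 adds only imaging at 6 months.
- Footnote d and Section 7.4 both start from a urinalysis that has already shown 2+, so neither can detect a first event.

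No routine urinalysis is scheduled between Day 29 and discontinuation.

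**3. How long is the gap?** Inputs from the documents: 28-day cycles, Cycle 2 Day 1 on Day 29, and 29 planned patients. The documents give no expected treatment duration, so I assume n = 2, 3, 6 and 12 completed cycles, with the discontinuation visit on Day 28n + 1. The ±7-day visit windows are ignored.

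- Interval under the plan: (28n + 1) − 29 = 28(n − 1) days
- Longest interval after Day 29 with testing every cycle: 28 days
- Extra untested time: 28(n − 1) − 28 = 28(n − 2) days
- Cycle Day 1 visits without the test: n − 2
- Ceiling on added tests if all 29 patients stayed on drug for n cycles: 29(n − 2)

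| Cycles (assumed) | Interval under plan (days) | Extra untested time (days) | Day 1 visits without test | Ceiling on added tests |
|---|---|---|---|---|
| 2 | 28 | 0 | 0 | 0 |
| 3 | 56 | 28 | 1 | 29 |
| 6 | 140 | 112 | 4 | 116 |
| 12 | 308 | 280 | 10 | 290 |

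**4. Cross-check at 180 days.** Section 9.1.3 foresees some patients still on drug at 180 days. Such a patient would pass five Day 1 visits without a urinalysis (Days 57, 85, 113, 141 and 169), and at least 180 − 29 = 151 days since the last scheduled test. This agrees with the six-cycle row: the end point moves from Day 169 to Day 180, which adds 11 days and the Day 169 visit.

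**The case against.** **A merged cell may have been lost in reading the PDF.** The three exceptions (TSH, urinalysis, pregnancy test) are adjacent and sit directly below Coagulation, whose Cycle 3+ entry is footnote j (if clinically indicated, at the investigator's discretion). A vertical merge whose mark survives only on its first row would look like this, and the eight-cell count does not exclude it. This stands as a possibility, but nothing shows that it happened. Even with footnote j, later testing would be discretionary and still not routine.

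**There is no internal contradiction.** Section 7.4 is conditional and covers any urinalysis, scheduled or not; it promises no testing frequency. That is correct. The point is a monitoring gap and does not depend on a contradiction.

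**Other safeguards exist.** Cycle 3+ visits keep vital signs, physical examination, AE review, and chemistry with albumin and creatinine. Section 8.3.6.3 asks for close monitoring, and patients are told to call with symptoms. Those already at 2+ on Day 29 get weekly repeats. These checks make late detection more likely than no detection at all, but none measures urine protein.

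**Frequency is unsupported.** Section 4.3.1 reports on 210 enrolled patients and does not name proteinuria. This stands and limits what can be said about how many patients are at risk.

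**The durations and the 28-day benchmark are the review's own choices.** Also true. At two cycles the excess is zero, and the 280-day figure needs about a year on drug.

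**The pregnancy test has the same blank cell, with a withdrawal rule behind it in Section 8.3.7.** That is fair and deserves a query, but it does not weaken the urinalysis point.

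**Conclusion.** The concern holds. As the plan reads, one routine urinalysis falls between the first dose and discontinuation, on Day 29, and the Section 7.4 hold has no scheduled trigger for proteinuria that starts later. For a patient treated six cycles this means 140 days between scheduled tests instead of at most 28; for three or twelve cycles it is 56 or 308 days. These figures rest on assumed durations, 28-day cycles and a discontinuation visit immediately after the last cycle.

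The likely harm is late detection in an unknown number of patients. The primary response-rate test and the sample size are untouched. The change should be made because it is cheap and supports a dosing rule the plan already contains. Confidence is medium, mainly because a merged table cell cannot be fully excluded.

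**What to change.** In Table 4, enter X with footnote i in the Cycle 3+ cell of the Urinalysis row, so that the test is done on Day 1 of each new cycle. Footnote k (every second cycle, with imaging) would also supply a scheduled trigger, but would leave intervals of 2 × 28 = 56 days. Footnote i fits better because drug is dispensed at each of those visits.

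The cost is one urinalysis per patient per cycle at a visit that already takes blood, with microscopy if the result is abnormal. The ceiling is 29, 116 or 290 added tests if all 29 patients stayed on drug for 3, 6 or 12 cycles. A 2+ result adds a spot ratio, a 24-hour collection and weekly repeats, all of which Section 7.4 and footnote d already require.

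As a separate query, ask the sponsor to confirm that the blank Cycle 3+ cells for TSH and the pregnancy test are intended.

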9.1 Study Periods

9.1.1 Screening Period (Days -28 to -1)

Prior to performing any study procedures, the Investigator, or designee, will obtain written informed consent from the patient as described in [Section 3.3](#). The patient's consent must be confirmed at the time of signature by the dated signature of the person conducting the informed consent discussions. A copy of the signed consent document must be given to the patient or the patient's legally authorized representative. "Legally authorized representative" means an individual or judicial or other body authorized under applicable law to consent on behalf of a prospective patient to the patient's participation in the procedure(s) involved in the research. The Investigator will retain the original signed consent document.

The specific Screening assessments are described in [Section 8](#). Results of all assessments/evaluations must be acceptable to the Investigator and to the Sponsor or their designee prior to treatment with study medication.

When all screening results are completed and eligibility is confirmed, the patient will be assigned a patient identification number.

9.1.2 Treatment Period

The assessments to be performed during the Treatment Period are described in [Section 8](#) and the timing of the assessments is provided in [Table 4](#). Assessments at each clinic visit following Day 1 must be completed within ± 3 days of the indicated visit day for Cycle 1 and each monthly visit (Cycle 2+) must be completed within ± 7 days of the indicated visit cycle (4-weeks).

9.1.3 End of Cycle 6 Assessment Time point

All patients will have radiographic assessments of their disease at 6 months/180 days unless CT scan has previously documented progression of their disease. For patients who are continuing to receive study drug at this time point, this radiographic assessment may be combined with their regular visit and list of assessments for the cycle.

9.1.4 End of Study Drug Administration Visit

End of study drug administration assessments will be completed for each patient as indicated in [Table 4](#).

9.2 Study Procedures

9.2.1 Pharmacokinetic analysis

Blood samples will be drawn from all the patients enrolled prior to the dosing at Day 1, Day 8 and Day 15 (steady state) of Cycle 1, and day 1 of Cycle 2, and Cycle 3, respectively as outlined in [Table 4](#).

4 mL blood will be collected in tubes containing heparin sodium. Following blood collection, samples will be cooled in an ice bath and centrifuged (at approximately 1500 rpm for 10 minutes) under refrigeration at a temperature of approximately 4°C within 30 minutes of collection. Plasma samples will be divided into 2 aliquots of approximately equal volume and stored in suitably labelled tubes at -80±15°C (within 45 minutes of blood sample collection), pending assay. Samples will remain in an ice bath until placement in a freezer.

Plasma samples will be retained and plasma concentrations of ENMD-2076 and its major active metabolite ENMD-2060 will be analysed. The effects of gender, age, body weight and CLcr (creatinine clearance) on the steady state plasma concentrations will be evaluated to explore the drug's exposure-response relationships.

(A manual for the Pharmacokinetic analysis will be provided)

9.2.2 Tissue biomarker analysis:

Formalin-fixed paraffin embedded archival surgical tumor tissue samples obtained from patients will be used for immunohistochemical analysis of key markers of proliferation (phospho-histone H3 [pHH3], Ki67), tumour microvessels (CD31) and p53. Following paraffin removal and subsequent rehydration of sections 5 lm thick, antigen retrieval is performed by incubating slides for 10 min at 100 °C in 10 mM sodium citrate, pH 6.0 (p53, pHH3, Ki67) or 10 mM Tris, 1 mM ethylene diamine tetra-acetic acid (EDTA), pH 9 (CD31). Slides are blocked in 10% donkey serum in phosphate buffered solution (PBS) for 1 h then incubated for 1 h with primary antibody diluted in 2% donkey serum-PBS. Antibodies and dilutions to be used are as follows: p53 mouse monoclonal clone DO-1 (1:2000), Santa Cruz; pHH3 (Ser10) mouse monoclonal (1:1000), Cell Signalling; Ki67 mouse monoclonal clone MIB-1 (1:200), Dako; CD31 mouse monoclonal clone JC70A (1:500), Dako.

Slides are incubated overnight with biotin conjugated donkey anti-mouse IgG (Jackson ImmunoResearch, 1:200), followed by incubation with horseradish peroxidase-conjugated streptavidin (Jackson, 1:200) for 1 h. After washing in PBS, slides are developed with 3,3' diaminobenzidine (Dako), followed by counterstaining with haematoxylin (Dako). All slides are digitally scanned using the ScanScope XT brightfield scanner (Aperio Technologies), with an Olympus 20 X/0.75NA objective lens (resolution ~0.5 microns/pixel). Images are visualized and analyzed using ImageScope (Aperio). Cells positive for pHH3 and Ki67 staining are counted using the accompanying Nuclear_v9 algorithm. The CD31 microvessel density (MVD) count is determined by locating three CD31- dense hotspots in each section and counting the number of CD31-positive loci in a high-power field area for each hotspot, then representing the average as number of microvessels (MV) per mm².

The tissue should be shipped to Memorial Sloan Kettering Cancer Center for subsequent biomarker studies and possibly other research.

